We will query CDW for 6 months following the date of each scheduled primary care visit to assess our primary outcome of deprescribing. Based upon findings in our pilot study, medication orders may not be discontinued in electronic health records even if discussions occur in the clinic visit (e.g., the PCP tells the patient to deprescribe but does not change the order). Notably, because our primary objective is to improve safe prescribing and reduce PIMs, pharmacy dispensing data best reflects our deprescribing outcome. As per our definition, either complete cessation or dose reduction will be fulfillment of our primary outcome.

Modeling our approach after the methods of Steinman, Sussman, and Martin, we will use non-refill of the medication in the 6 months following the primary care appointment as our a priori definition of cessation, based upon dispensing dates.^{4,5} Per VA Pharmacy policy, medications are only refilled upon request, and therefore, non-refill of a medication can indicate that it was discontinued, it expired (typically one year after it was ordered), or the patient did not refill it. If the medication continues to be dispensed, we will determine any reduction in the total daily dose, indicating de-escalation (one component of our deprescribing definition). An

exception to the de-escalation rule will be for insulin, where only complete cessation will qualify since dose changes are less likely to be reflected in the order compared to oral medications.

Consistent with our conceptual framework, we will also assess patient and provider factors that may influence deprescribing. Patient factors will be obtained from CDW, and will include age, race, sex, Elixhauser comorbidities in the two years prior to the scheduled primary care visit. Provider factors include sex, discipline, age, and site.

To assess potential ADWEs, we will ascertain if the deprescribed medication is subsequently restarted or returns to original dosing. We will then query CDW for diagnoses of GI bleeding for the PPI cohort, diabetic ketoacidosis or hyperosmolar hyperglycemic state for the DM cohort, and seizure for the gabapentin cohort in the year following the index visit. Note, we consider substitution to a lower potency medication (e.g., histamine-2 receptor antagonist for a PPI) to be a neutral or desirable event and not an ADWE.

Statistical Analysis Plan (see attached statistical analysis plan for greater detail)

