Official Title: Engaging Patients to Promote Deprescribing

NCT Number: NCT04294901

Document Date: November 14, 2019

Statistical Power

Based on fiscal year (FY) 2017 data, we estimated that we would mail brochures to at least 1,990 PPI patients, 894 Diabetes-Hypoglycemia patients, and 758 Gabapentin patients during the study. For apriori statistical power analyses, we made the following assumptions based on our pilot data: an overall baseline deprescribing rate of 4.21%, a conservatively high intraclass correlation coefficient (ICC) of 0.05 (for non-independence among patients of the same provider), an average of 20 eligible patients per PCC or WHC provider, and a 20% attrition rate (i.e., patients who receive the intervention brochure but do not attend their clinic visit). With these assumptions, we determined that we would have 80% power (for two-tailed tests at $\alpha=0.05$) to detect deprescribing rates following the intervention as small as 6.55% overall for these low-end estimates of our projected sample. Moreover, even at these low-end estimates of the projected sample size, we determined we would have 80% power to detect an overall deprescribing rate as low as 15% among the combined intervention cohorts even if the ICC was as high as 0.1, the baseline deprescribing rate was as high as 10%, and/or the attrition rate was as high as 40%. Notably, a deprescribing rate of 15% was reasonable to expect given that we found similar or higher rates in our pilot study.

We conducted analyses using SAS.³

Endpoints & Covariates

The primary hypothesis was deprescribing would be greater for Veterans receiving the intervention brochure than for those in the historical control group.

The primary outcome was binary: deprescribing versus not, assessed via pharmacy dispensing data from the VA Corporate Data Warehouse (CDW). More specifically, six months from the index date, an analyst queried the CDW to determine medication outcomes (e.g., complete deprescribing, dose reduction). We selected 6 months because prescriptions are often filled as a 90-day supply and using a shorter observation window might not fully identify that the prescription was not refilled. We removed patients who died within six months from their index data from intervention and historical controls at the analysis stage to avoid misattributing deprescribing to the intervention rather than death.

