To identify dose reductions, we calculated the total daily dose (TDD) of the target medication as [dose*(quantity/days supplied)].^{1,2} Substitutions within a medication drug class (e.g., pantoprazole to omeprazole) were standardized to one medication within each class. We only compared TDD at 6 months to that at the index visit for oral medications because insulin dose adjustments are not consistently documented within the electronic health record. Combination insulin products were separated into their long acting and short acting components and analyzed separately. We allowed a 10% buffer for days' supply of PPI, sulfonylurea, and gabapentin (e.g., 33 days for a 30-day supply) to account for missed doses and 100% buffer for insulin due to dispensing requirements (e.g., minimum vials dispensed regardless of dose).

Patient factors and provider characteristics (age, gender, profession) were included as covariates in the model. Based on our conceptual model and using data from CDW, patient factors included age, race, sex, and Elixhauser comorbidities in the year prior to the scheduled primary care visit.^{4,5}

Additionally, we planned to examine whether the effectiveness of the brochure intervention was associated with target medication.

Interim & Final Analysis

Our primary comparisons were between “brochure-intervention” patients and “historical control” patients (matched in terms of eligibility) from the same primary care provider. To investigate the impact of the intervention brochure on deprescribing, Hierarchical Generalized Linear Modeling (HGLM) was used to account for the nesting of patients within providers. This approach provided information not just about the average effectiveness of the intervention, but also about how much variation there is in the intervention impact across providers. In all models, Level 1 (patient-level) intercepts and slopes were treated as random effects, and parameters were estimated with robust standard errors. Using this approach of nesting patients within providers at intervention sites, for our primary analysis, we compared the likelihood of deprescribing among patients in the pre-intervention (“historical”) period to that for patients in the intervention periods who were mailed the brochure. We predicted that intervention patients would be significantly more likely to have deprescribing than patients in the pre-intervention period with the same eligibility criteria. We then examined whether the

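### The restart measure cannot see a return to the original dose within six months, so a low restart count would not show that deprescribing was tolerated

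*Protocol*

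**What the plan says.** The protocol (Study Measures) gives two routes into the deprescribed class. For cessation, "we will use non-refill of the medication in the 6 months following the primary care appointment as our a priori definition of cessation". For de-escalation, "If the medication continues to be dispensed, we will determine any reduction in the total daily dose, indicating de-escalation". Insulin has only the first route: it is the exception "where only complete cessation will qualify". The SAP (Endpoints & Covariates) fixes the time of the dose comparison: "We only compared TDD at 6 months to that at the index visit for oral medications".

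For possible adverse drug withdrawal events the protocol takes two steps. The first is restart: "we will ascertain if the deprescribed medication is subsequently restarted or returns to original dosing". No time window is given. The second is a diagnosis search, which begins "We will then query CDW for diagnoses of GI bleeding for the PPI cohort", names the matching diagnoses for the diabetes and gabapentin cohorts, and runs "in the year following the index visit". Separately, the Safety Monitoring Plan looks each quarter, in every recruited subject, for emergency and hospital visits for the same kinds of event.

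The SAP contains no analysis of restart or of withdrawal events.

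**The concern.** The restart check starts from a medication that has been deprescribed. The only definition of deprescribed in the documents is the primary outcome, and for a full return to treatment that outcome is met only if the patient has not resumed by month 6. Early failure therefore removes a patient from the group in which failure is counted.

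This matters because the protocol's Risks section says that return of the original symptoms is commoner than a withdrawal reaction. Symptom return is not among the diagnoses searched for. Restart is the only planned measure that could show it. The same section foresees patients stopping on their own after reading the brochure, and a stop followed by an early refill is one trace this could leave in dispensing data. If such episodes were frequent, the trial could still report few restarts.

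**Working it through.** **Step 1: follow typical courses through the definitions.**

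| Course after the index visit | Refill within 6 months | Daily dose at 6 months against index | Class | Can later count as a restart |
|---|---|---|---|---|
| Oral drug stopped, refilled at original dose in month 4 | Yes | Same | Not deprescribed | No |
| Oral dose cut, restored by month 6 | Yes | Same | Not deprescribed | No |
| Insulin stopped, refilled in month 4 | Yes | Not compared | Not deprescribed | No |
| Oral drug stopped, resumed at a lower dose in month 4 | Yes | Lower | Deprescribed (de-escalation) | Yes |
| Any drug not refilled for 6 months, refilled in month 8 | No | None dispensed | Deprescribed | Yes |
| Oral dose cut and still lower at month 6, restored in month 9 | Yes | Lower | Deprescribed | Yes |

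The first three rows are the gap. A full return to treatment is visible only after month 6.

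**Step 2: check whether serious events share the gap.** They do not. The diagnosis search is set out by medication cohort, not by deprescribing status, and its year includes months 0–6. The quarterly check covers all who were recruited. A patient who stops, bleeds and refills in month 4 remains in both. The two sections do differ in event source (diagnoses against emergency and hospital visits) and in wording (GI bleeding against upper GI bleeding), and neither says whether historical controls are included.

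**Step 3: possible size.** The plan gives no restart figure, so there is none to reproduce, and what follows is illustration only.

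*Counts.* The SAP projects 1,990 + 894 + 758 = 3,642 brochures. With its 20% attrition, 3,642 × 0.8 = 2,914 patients attend. If a share f of all initial deprescribing fails before month 6 and D patients are recorded as deprescribed, the unrecorded failures number D × f/(1 − f).

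| Recorded rate (SAP) | D | f = 5% | f = 10% | f = 20% | f = 30% |
|---|---|---|---|---|---|
| 6.55% | 2,914 × 0.0655 = 191 | 10 | 21 | 48 | 82 |
| 15% | 2,914 × 0.15 = 437 | 23 | 49 | 109 | 187 |

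The values of f are assumed.

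*Timing.* Suppose full-dose restarts over 12 months are either uniform or exponential with median m months. The share falling by month t is t/12, or (1 − 0.5^(t/m))/(1 − 0.5^(12/m)).

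| Assumed timing | Months 0–6 | Of which 0–3 | Of which 3–6 |
|---|---|---|---|
| Uniform | 50% | 25% | 25% |
| Exponential, m = 6 | 67% | 39% | 28% |
| Exponential, m = 3 | 80% | 53% | 27% |
| Exponential, m = 2 | 89% | 66% | 23% |

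The SAP says that fills are often for 90 days. With a 90-day fill at the visit, a stop and restart in months 0–3 leaves no fill of its own; at most the next fill comes late. That part is mainly a limit of dispensing data. The part due clearly to the definition is months 3–6, about 23% to 28% under these assumptions.

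**The case against.** The strongest reply is that safety is already covered for everyone. For serious events that is right. A reader might infer that withdrawal harm is sought only in patients classed as deprescribed, or that the plan would make serious withdrawal events look rare whatever happened. The documents do not support either. The word that opens the diagnosis search could suggest a follow-on from the restart check, but the search names whole cohorts, and the Safety Monitoring Plan settles the matter for emergency and hospital visits.

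Three other strong readings also fail.

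- That anyone who resumes within six months is excluded: an oral drug resumed at a lower dose still counts as de-escalation.
- That fatal events drop out of the safety data: the SAP says "We removed patients who died within six months from their index data from intervention and historical controls at the analysis stage", but it gives as the reason that death might be mistaken for deprescribing, and the sentence sits with the primary outcome. Nothing extends it to the diagnosis search or the quarterly check.
- That 50% to 89% of restarts are missed: those shares come from assumed timing, and much of each lies in months 0–3, where fills show little.

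It is also fair to say that the protocol never states that a deprescribed medication means one meeting the six-month outcome. That is an inference, though no other definition is given. Finally, this is a secondary safety measure, and no primary result depends on it.

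None of this closes the restart gap. The serious-event checks do not capture symptom return, do not link events to stopping or restarting, and state no comparator.

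**Conclusion.** The point holds for restart and only for restart. Followed as written, the measure records a return to the original dose within six months, or any insulin refill in that time, as no deprescribing at all. A low restart count could not support a statement that deprescribing was tolerated. The number affected cannot be derived from the documents; the counts and percentages above show only what assumed values would imply. The conclusion rests on reading the deprescribed class as the primary-outcome class.

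The primary outcome, its death exclusion and the power calculation are unaffected. The change is worth making because restart is the only planned view of the commoner consequence of stopping.

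**What to change.** Keep the six-month primary outcome and its death exclusion as they are, and specify the safety measures separately.

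1. Define restart from any stop or reduction seen after the index visit: a dispensing gap longer than the days' supply plus the SAP's buffer, or a lower-dose fill of an oral drug, followed by a refill or a return to the index daily dose at any time up to month 12. Report months 0–6 and 6–12 separately, for brochure patients and historical controls.
2. Run the one-year diagnosis search in historical controls as well as mailed patients, and state that the primary-outcome death exclusion does not apply to it.
3. Reconcile the Study Measures section and the Safety Monitoring Plan on population, event source and the wording of the bleeding event.

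The cost is SAP wording and further programming on Corporate Data Warehouse records. The SAP is written in the past tense, so the analysis should be labelled as an addition.

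There are limits. Some late refills will count as restarts; comparison with controls helps to interpret this. A stop and restart within one filled supply still cannot be identified as such. The buffer also matters: a 90-day oral fill is exceeded after 90 × 1.10 = 99 days, but a 90-day insulin fill with the 100% buffer only after 90 × 2 = 180 days. On such fills the month 0–6 count would be almost blind for insulin, and the report should say so.

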It is possible that Veterans could feel discomfort receiving information about their medications, expressing their beliefs and perspectives, or have concerns that their subsequent health care services will be affected. Bringing the issue of potential medication overuse to Veterans' attention may also lead them to worry that they are taking too many medicines or that the targeted medications (PPIs, diabetes medications, or gabapentin) may have caused them harm.

The intervention could lead to the actual discontinuation of unnecessary medications as intended; nonetheless, there is a slight possibility that the intervention could unintentionally lead to discontinuation of medications that are necessary or that the discontinuation of medications perceived as unnecessary could actually result in adverse drug withdrawal events. It is also possible that patients will stop a medication after receiving the brochure but without consulting their primary care provider.

The risks of deprescribing medications include, but are not limited to, adverse drug withdrawal reactions and return of a medical condition. Adverse drug withdrawal reactions are rare, especially in comparison to adverse drug events. It is more common for patients to experience a return of symptoms for which the medication was initially prescribed. Serious adverse events resulting from inappropriately discontinuing a medication include upper gastrointestinal bleeding for the PPI cohort, diabetic ketoacidosis or hyperosmolar hyperglycemic state for the DM cohort, and seizure for the gabapentin cohort.

Risk from breach of confidentiality – The risk to participants includes potential compromise of confidential information; however, the use of VA data in research analyses similar to those proposed is standard practice and there are no viable alternatives to obtain this quantity and quality of data. We will take all actions required to protect the security and integrity of confidential and personal health information.

Procedures to Minimize Risk

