Veterans receiving the intervention (brochure) and survey – Exclusion criteria have been carefully incorporated to help minimize Veteran risk prior to enrollment. Further, as noted, we are not randomizing patients to have medications withdrawn. The primary intervention is distribution of information directly to patients. It is important to note that the decision to deprescribe or not remains in the purview of the patient-provider dyad. We will provide a brief cover letter when sending the medication-specific brochure to patients, and the medication-specific brochure states multiple times to not decrease or discontinue a medication without first consulting with a clinician. We are also mailing the brochures two weeks prior to a primary care visit, so if patients decide they want to stop a medication, they will already have an appointment scheduled. Taken together with the fact that patients and providers already have the ability to make deprescribing decisions, the risk of this study is not greater than current standard practice.

Risk from breach of confidentiality – In order to assure appropriate research subject selection and high-quality data collection, all study personnel will undergo training in the study protocols. We will take all necessary steps to ensure the protection of confidential information in accordance with VA regulations and other applicable laws. All identifiable data will be protected from improper use or disclosure. Only research team members will have access to data. We will enter survey data into an electronic database with a unique identifier, removing any Protected Health Information (PHI). We will store all electronic data entirely within the VA network, which is protected by firewalls. User identification codes limit access to specific directories and files. We will not include names on audio-recordings or transcriptions, and publications will not identify individual participants or the sites from which they were recruited. We will not disclose identifiable information to any other person or entity outside VA, except as required by law, for authorized oversight of this research study, or for approved use in another study by an IRB. We will store physical data in locked cabinets within the Section of General Internal Medicine and Center for Healthcare Organization and Implementation Research (CHOIR) offices at VA Boston

Potential Benefits

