Per instructions of the VA HSR&D Program, the full Data Analysis Plan has been submitted to the Data Safety Monitoring Board (DSMB) using the Just-In-Time (JIT) document manager. Because the intervention described is an educational outreach to patients, there is minimal risk since clinical providers retain complete authority to deprescribe, de-escalate, and resume medications per their clinical judgement. However, it is possible that deprescribing could lead to adverse drug withdrawal. We expect these to be extremely rare occurrences, as we are identifying Veterans likely to be over-treated and further excluding populations for whom the medications are indicated. Thus, we will assess for serious adverse drug withdrawal events, specifically looking for emergency department and hospital visits for upper gastrointestinal bleeding for the PPI cohort, diabetic ketoacidosis or hyperosmolar hyperglycemic state for the DM cohort, and seizure for the gabapentin cohort on a quarterly basis for all recruited subjects.

Monitoring progress reports will be submitted to regulatory bodies (e.g., IRB) as requested and/or required. This will serve as a method for identifying systematic problems and allow the study team to identify and resolve problems and continuously maintain and improve data quality and Veteran safety. Additionally, we will schedule weekly team meetings to be led by the study PI and include all study personnel directly involved in enrollment, data collection, data entry and the intervention protocol. These team meetings will allow the study PIs to keep track of enrollment numbers, data integrity (e.g., reasons for missing data), and protocol implementation challenges that need to be addressed in a timely manner.

Adverse Event/Unanticipated Problems Reporting Plans

The Principal Investigator at VABHS will report Unanticipated Problems, Adverse Events, and safety monitors' reports to the IRB in accordance with VHA Handbook 1058.01 and VABHS IRB SOP. This is a multi-site study, but all procedures will be conducted at VABHS and thus oversight remains with the VABHS IRB.

References

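### The adverse drug withdrawal search opens at the visit, although brochures are mailed two weeks earlier; coverage of the interval between is not stated, and the bleeding event is named in two ways

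*Protocol*

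**What the plan says.** Protocol, Study Measures, assesses adverse drug withdrawal events (ADWEs) in two steps. First, "we will ascertain if the deprescribed medication is subsequently restarted or returns to original dosing". Then the investigators will "query CDW for diagnoses of GI bleeding for the PPI cohort", with ketoacidosis or hyperosmolar state for the diabetes cohort and "seizure for the gabapentin cohort in the year following the index visit".

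Protocol, Procedures to Minimize Risk, gives the timing of the intervention: "We are also mailing the brochures two weeks prior to a primary care visit". Under Risks, the protocol accepts that "It is also possible that patients will stop a medication after receiving the brochure but without consulting their primary care provider". The note on cognitive impairment under Recruitment likewise considers diabetes patients who stop before talking to their provider.

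Protocol, Safety Monitoring Plan, describes a second search, "specifically looking for emergency department and hospital visits for upper gastrointestinal bleeding for the PPI cohort", with the same diabetes and gabapentin conditions as above, run "on a quarterly basis for all recruited subjects". It states neither when the search starts for a subject nor when it ends. The Risks section also names upper GI bleeding.

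The SAP has no ADWE definition, window or analysis. Its Statistical Power section assumes that 20% of patients who are sent a brochure do not attend the visit.

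**The concern.** The brochure is the intervention, so exposure starts when it arrives, not at the appointment. The interval before the appointment is when a patient can act on the brochure with no clinician yet involved, and the protocol names exactly that risk. The Study Measures search leaves the interval out.

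The restart step in the same section does not close the gap. Take a patient who stops on reading the brochure, is admitted before the appointment, is put back on treatment, and then refills at the same dose. That patient meets neither the cessation nor the dose-reduction definition, so there is no deprescribed medication to follow for restart. The admission itself precedes the diagnosis window.

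Two further points are left open. The primary outcome is anchored to the scheduled visit, but the ADWE search is anchored to an index visit that is not defined for someone who did not attend. And the two sections name the bleeding event differently, with nothing in either document to say how the two searches relate.

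The study has no stopping rules and requests a waiver of informed consent, so event ascertainment carries much of the safety case.

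**Working it through.** The plan states no ADWE rate or expected count, so there is no figure of its own to reproduce. The check sets the two searches side by side and sizes the gap.

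**The two searches**

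| | Study Measures | Safety Monitoring Plan |
|---|---|---|
| Bleeding event | GI bleeding, site not given | upper GI bleeding |
| Other conditions | ketoacidosis/hyperosmolar state; seizure | the same |
| Care setting | none named | emergency department and hospital |
| Start | index visit | not stated |
| End | one year later | not stated |
| Restart or return to original dose | yes | no |
| Historical controls | not stated | not stated |

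**Inputs**

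- Mailing to visit: 14 days (Procedures to Minimize Risk).
- Search window: 365 days (Study Measures).
- Low-end mailings: 1,990 + 894 + 758 = 3,642 (SAP, Statistical Power).
- Assumed non-attendance: 20% (same section).

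**Share of post-mailing time outside the window**

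- gap / (gap + 365) = 14 / 379 = 3.7%.
- If postal delay leaves only 7 of the 14 days after delivery (an assumption): 7 / 372 = 1.9%.

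**Person-time outside the window**

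- 3,642 × 14 / 365.25 = 139.6, about 140 patient-years. This counts every mailed patient from the mailing date. It is not time off the drug.
- Study Measures can also be read as querying diagnoses only in patients who were deprescribed. At the SAP's rates of 6.55% and 15%, that gives 139.6 × 0.0655 = 9.1 and 139.6 × 0.15 = 20.9 patient-years.

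**Patients without an attended visit**

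- 3,642 × 0.20 = 728.

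**Events in the gap, illustration only**

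The documents call ADWEs extremely rare but give no rate. Assume annual rates of 0.1% to 2% and a constant hazard.

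- 3,642 mailed: 139.6 × 0.001 = 0.14, to 139.6 × 0.02 = 2.8 events.
- If all of the protocol's maximum of 6,800 subjects were mailed: 6,800 × 14 / 365.25 = 260.6 patient-years, so 0.26 to 5.2 events.

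A constant hazard may understate the gap, since these are the first days after a possible unsupervised stop. The documents do not allow that to be quantified.

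**The case against.** The strongest reply is that the Safety Monitoring Plan already looks for emergency and hospital visits in all recruited subjects and is not tied to the visit. An admission before the appointment is the kind of event it seeks. This stands in part: a reader might infer that early events are lost to the trial altogether, and the text does not support that. They are excluded from the Study Measures outcome. Whether surveillance catches them depends on a start date that is not given, and a case found there would have no stated comparator.

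Second, a reader might infer that two different bleeding counts are an error in themselves. They need not be. Surveillance of serious events can properly be a subset of a broader measure, and the omission of the word upper in Study Measures may be shorthand. No code list is shown, so it cannot be said that lower-tract, outpatient or history codes will be counted. What stands is that the difference in terms and the relation between the searches are unexplained.

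Third, a reader might infer that the plan is biased towards finding no safety signal. Neither document specifies a between-group ADWE analysis. Unrelated events that occur equally in both groups pull a ratio towards one but leave a risk difference unbiased, with lower precision. Without an estimand, no direction can be claimed.

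Fourth, the visit anchor is the same for historical controls, who have no mailing date. That is a real merit, and any change must preserve it. Finally, the index visit may simply mean the scheduled date, which exists for non-attenders too; the text leaves this unclear rather than excluding them.

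**Conclusion.** The concern holds as a gap in one safety measure. As written, the Study Measures search excludes events between mailing and visit, an interval in which the protocol expects that some patients may stop unsupervised. The Safety Monitoring Plan does not clearly cover that interval. The anchor date is undefined for about 728 of 3,642 mailed patients if 20% do not attend, and the bleeding term differs between sections.

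The gap is small in calendar terms: at most 14 of 379 days (3.7%), or about 140 patient-years at the low-end mailing estimate, before postal delay. It rests on a uniform two-week lead and on every mailed patient being searched. It is an upper bound on unobserved time for those mailings, not a count of missed events, which cannot be sized without a rate. The documents do not show that early events go wholly undetected, that the two counts ought to agree, or that the result leans either way. The change is still worth making because it is cheap and covers a risk that the protocol names.

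**What to change.** In Protocol, Study Measures, and in a short ADWE section added to the SAP:

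- Define the index visit as the date of the scheduled appointment, kept or not.
- Start the diagnosis search at the mailing date and run it to 12 months after the scheduled visit, for every mailed patient whether or not the visit took place.
- In historical controls, start the search 14 days before the scheduled visit so that the windows match.
- Report events between mailing and visit on a separate line.
- Reconcile the bleeding term across Study Measures, Risks and the Safety Monitoring Plan, with upper GI bleeding reported as the named event.
- State that the Safety Monitoring Plan search is the serious (emergency or hospital) subset, and give its start and end dates. Keep outpatient-diagnosed events in the Study Measures count.

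The cost is wording in two documents, a changed start date in an existing data warehouse query and slightly more query work. No new data collection is needed. The drawback is a constructed start date for controls: where actual mailing departs from 14 days, the two windows will differ slightly.
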